2.2 Secondary objectives

1. To compare the quantitative primary and secondary results of MagnetOsTM Granules to the results of Attrax® Putty from the AxA study (unpaired);
2. To investigate the relation between successful posterolateral fusion and interbody fusion, assessed at the one-year CT-scans used for the primary objective;
3. To compare the posterolateral spinal fusion rate of both MagnetOsTM Granules and autograft at one year with the fusion rates after two years, by using CT-scans;
4. To investigate the effect of blinding on perceived donor site pain, based on outcome measures reported by patients unblinded to the iliac crest donor site in comparison to these outcomes of the blinded patients from the AxA study;
5. To combine the study populations of the current study and the AxA study to investigate a) adjacent segment disease, in relation to length of construct and sagittal balance and b) risk factors for failures.

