Although iliac crest donor site morbidity is often reported by patients, the relevance of donor site pain is disputable when the bone is harvested via the same incision as used for the spinal fusion.³ The preliminary results of the AxA study indeed indicate that there is no relation between the real donor site and the iliac crest that is indicated by blinded patients. To determine if the often reported high incidence of donor site pain can be explained by the knowledge of the patient where the bone graft was taken, we will not blind the patients for the donor site in this study. The outcomes measures reported by patients unblinded to the iliac crest donor site will be compared to the outcomes of the blinded patients from the AxA study.

5. Combine the study populations of the current study and the AxA study

To combine the study data of both the current study and the AxA study will allow investigations on more infrequent phenomena on a relatively large population. Such a phenomenon is for example adjacent segment disease. This is a longterm complication where the adjacent joints and intervertebral disc may wear faster and cause degenerative disease. The occurrence of adjacent segment disease may be related to length of the construct and restoration of the sagittal balance. The occurrence of typical complications like infection and pseudoarthrosis can be related to risk factors like comorbidities, smoking, length of instrumented segment and so on.

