4.4 Sample size calculation

The primary objective of this study is to demonstrate that treatment with MagnetOsTM Granules is non-inferior to autograft to obtain bony fusion in the spine. The primary outcome is the rate of successful posterolateral bony fusion after one year, assessed at CT-scans. Fusion will be scored binomially and non-inferiority of fusion in the MagnetOs condition will be assessed using a McNemar's test.

Based on literature^{6,28-30,34} and the preliminary results of the AxA study, we estimate a fusion percentage of 50% for unilateral grafting after one year, and a 70% concordance between the left and right side of the fusion trajectory (i.e. both sides fused or non-fused). The non-

inferiority margin is set at an absolute 15% less effectiveness in the MagnetOs condition after one year, which corresponds with 15% less posterolateral sides that are judged as fused. In other words, the rate of fused posterolateral sides in the MagnetOs condition should be more than 35% if the autograft condition shows 50% fusion. We argued that the percentage of the iliac crest graft related complications, ranging from 5% major complications to 40% minor complications, may justify 15% less fusion in a condition that eliminates these complications.

Based on a 1:1 paired assignment of MagnetOsTM Granules to the control condition with autograft, a power of 80%, a one-sided alpha of 0.05 and the non-inferiority margin of 15%, the required sample size for the primary outcome is 84 patients (see Appendix A). We assume that approximately 15% of the included patients will not be evaluable after one year. The intra-patient analyses are not possible when the fusion area has to be revised or when a deep wound infection has occurred and considerable amounts of graft material have to be removed (expected percentage 2-5%). Other failures are lost to follow-up or bad scan quality. Therefore, the total number of patients to be enrolled will be 100.

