7.1.2 Secondary study outcomes

1. Comparison of the quantitative primary and secondary results of MagnetOsTM Granules to the results of AttraX® Putty from the AxA study (unpaired);
2. Relation between successful posterolateral fusion and interbody fusion at one-year follow-up (assessed on CT-scans);
3. Posterolateral spinal fusion rate at two years follow-up compared to the fusion rate at one-year follow-up (assessed on CT-scans);
4. Effect of blinding on perceived donor site pain;
5. Incidence of long-term complications and relation with risk factors in the combined population of this study and the AxA study.

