7.3.1 Baseline data

After enrollment (see Chapter 10 for the recruitment and consent procedure), a preoperative baseline evaluation will be performed and the following data will be collected (CRF A):

- Month and year of birth
- Gender
- Smoking
- Pre-operative diagnosis
- Prior treatment to affected spinal levels
- Concurrent medical conditions
- ASA classification
- Disease related medication use (including NSAID use)
- Questionnaires
 - EQ-5D-5L
 - ODI
- VAS pain score
 - Back pain related to diagnosis
 - Leg pain related to diagnosis
 - Pain in left iliac crest
 - Pain in right iliac crest
 - Pain drawing

The EQ-5D-5L is a standardized instrument for use as a measure of health outcome. Applicable to a wide range of health conditions and treatments, it provides a simple descriptive profile and a single index value for health status that can be used in the clinical and economic evaluation of health care as well as population health surveys. The Oswestry Low Back Pain Disability Index (ODI) is an evaluation questionnaire related to patient perception of the effect of his/her current low back pain on activities of daily living. A Visual Analogue Scale (VAS) will be used to record back pain, leg pain and iliac crest pain at the left and right side at all evaluation points. As a supplement, patients will be asked to make a pain drawing to get a graphic representation of the pain and its physical distribution.

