7.3.3 Planned follow-up moments

The subsequent follow-up moments will take place at the outpatient clinic and are based on the standard care at the UMC Utrecht. The data described below will be collected at 6 weeks, 3 months, 1 year and 2 years postoperatively. The questionnaires, CT-scan at 2 years follow-up in case of no or doubtful fusion at 1 year follow-up, and depending on the local follow-up protocol the CT-scan at one year follow-up and/or X-ray at two years follow-up, are extra for this study. In addition to the baseline questionnaires, treatment satisfaction will be assessed with a Numeric Rating Scale (NRS).

6 weeks (±14 days; CRF C)

- Complications / (serious) adverse events
- Disease related medication use (including NSAID use)
- Questionnaires
 - EQ-5D-5L
 - ODI
 - NRS satisfaction
- VAS pain score
 - Back pain related to diagnosis
 - Leg pain related to diagnosis
 - Pain in left iliac crest

- Pain in right iliac crest
- Pain drawing
- Imaging
 - Standing anteroposterior and lateral radiographs
- Radiologic evaluation by treating surgeon (indications for failure or deformation / instability)

3 months (\pm 21 days; CRF D)

- Complications / (serious) adverse events
- Disease related medication use (including NSAID use)
- Questionnaires
 - EQ-5D-5L
 - ODI
 - NRS satisfaction
- VAS pain score
 - Back pain related to diagnosis
 - Leg pain related to diagnosis
 - Pain in left iliac crest
 - Pain in right iliac crest
 - Pain drawing
- Imaging
 - Standing anteroposterior and lateral radiographs
- Radiologic evaluation by treating surgeon (indications for failure or deformation / instability)

1 year (12-15 months; CRF F)

- Complications / (serious) adverse events
- Disease related medication use (including NSAID use)
- Questionnaires
 - EQ-5D-5L
 - ODI
 - NRS satisfaction
- VAS pain score
 - Back pain related to diagnosis
 - Leg pain related to diagnosis
 - Pain in left iliac crest

- Pain in right iliac crest
- Pain drawing
- Imaging
 - Standing anteroposterior and lateral radiographs
 - CT-scan
- Radiologic evaluation by treating surgeon (indications for failure or deformation / instability)
- Fusion assessment based on CT-scan by treating surgeon per level and per side in three planes, without the distinction between graft-related or non-graft-related fusion as described in Appendix C.

2 years (22-26 months; CRF G)

- Complications / (serious) adverse events
- Disease related medication use (including NSAID use)
- Questionnaires

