9.3 Analysis of secondary outcomes

1. To compare the quantitative primary and secondary results of MagnetOs™ Granules to Attrax® Putty a McNemar's test will be used as well as the mentioned GEE model;
2. As mentioned for the primary analysis, the odds-ratios and 95% confidence intervals for fusion rates of MagnetOs™ Granules and autograft will be calculated by using the GEE model. This model also allows to assess the effect of an additional interbody fusion;
3. For the comparison of the fusion rate after two years, the same method as for the primary efficacy analysis will be used;
4. VAS pain scores will be analyzed using the paired t-test, or Wilcoxon signed rank test in case of not-normally distributed data. To investigate the effect of blinding on perceived donor site pain, pain scores reported by the patients of this study and the AxA study will be compared using the unpaired t-test or Mann-Whitney U test.
5. To investigate risk factors of both study populations regression analysis will be done.

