9.4 Other study parameters

The following information will be reported and reviewed, but will not influence the comparisons between the treatment conditions as this is an intra-patient model.

- Demographics
- Nicotine use
- Pre-operative diagnosis
- Medical history
- Concurrent medical issues
- ASA classification
- Disease related medication use
- NSAID use
- Perioperative data
- Length of hospital stay
- EQ-5D-5L
- ODI
- Pain drawing
- NRS satisfaction

The clinical outcome measures, the EQ-5D-5L, ODI and VAS, will be analyzed with repeated measurements to assess changes over time. For continuous data, an independent t-test or Mann Whitney U test (depending on the distribution of the data) will be used to compare the

clinical outcomes of fused and non-fused patients. For categorical data, the Chi-square test will be used. A logistic regression analysis will be performed to analyze the effects of smoking and NSAID use on fusion status.

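### The donor-site pain comparison with the AxA study uses two-sample tests on a score recorded for two crests at four postoperative visits, and no deciding visit, score or overall contrast is named

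*Combined protocol and SAP*

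**What the plan says.** The question is secondary objective 4 in section 2.2: "To investigate the effect of blinding on perceived donor site pain, based on outcome measures reported by patients unblinded". Section 7.1.2 lists it as outcome 4, "Effect of blinding on perceived donor site pain", with no time point, although outcomes 2 and 3 in the same list name theirs. Section 2.3 gives the purpose: "To determine if the often reported high incidence of donor site pain can be explained by the knowledge of the patient" of where the graft was taken.

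Section 7.3.1 provides for VAS scores of "iliac crest pain at the left and right side at all evaluation points". Section 7.3.3 sets the schedule: "The data described below will be collected at 6 weeks, 3 months, 1 year and 2 years postoperatively". Table 7.1 shows no questionnaire at the 1-5 day visit. Each patient therefore has up to eight postoperative crest scores, four visits by two sides.

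The between-study analysis is one sentence in section 9.3 item 4: "pain scores reported by the patients of this study and the AxA study will be compared using the unpaired t-test or Mann-Whitney U test". Section 9.4 adds: "The clinical outcome measures, the EQ-5D-5L, ODI and VAS, will be analyzed with repeated measurements to assess changes over time". Appendix A does not mention the comparison.

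**The concern.** An unpaired t-test or a Mann-Whitney test needs one number per patient, and up to eight are available. The plan gives no deciding visit, no rule for combining left and right, no summary over time, no significance level and no multiplicity rule. The repeated-measures analysis in section 9.4 would use all visits, but its stated purpose is change over time, not the contrast between studies.

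Section 2.3 intends the result to answer an explanatory question: whether reported donor-site pain comes from the patient knowing the harvest site. With nothing fixed in advance, a difference at a single visit could be presented as that answer. The comparator is also partly known already. Section 1 says that one-year AxA follow-up is complete, and section 2.3 cites preliminary AxA findings on donor-site pain. A visit or score chosen later would be chosen with one of the two cohorts at least partly seen.

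**Working it through.** **The plan's own figures.** The plan gives no sample size, power or error rate for this comparison. Its only stated error rate belongs to the primary test in section 4.4: "a power of 80%, a one-sided alpha of 0.05 and the non-inferiority margin of 15"%. That calculation reproduces. (1.645 + 0.842)² × 0.30 / 0.15² = 82.4, so 83 by normal approximation, and the exact power of the paired score test at n = 84 is 0.80098, the entry in Appendix A. It does not bear on donor-site pain.

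**Inputs**
- Postoperative visits with a crest score: 4 (section 7.3.3). Crest scores per visit: 2 (section 7.3.1).
- Assumed, because the documents do not give them: two-sided 5% per test; the between-visit correlation ρ; the same four visits in AxA; and a reading in which any one significant visit counts as a blinding effect.

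**False-positive chance.** With independent visits it is 1 − 0.95⁴ = 18.5%. With a common correlation ρ it is P(max |Z| > 1.96) over k equicorrelated standard normal statistics, found by numerical integration:

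| ρ | k = 4 (one score per visit) | multiple of 5% | k = 8 (both crests) |
|---|---|---|---|
| 0 | 18.5% | 3.7 | 33.7% |
| 0.3 | 17.4% | 3.5 | 30.0% |
| 0.5 | 15.6% | 3.1 | 25.0% |
| 0.7 | 13.0% | 2.6 | 19.1% |
| 0.9 | 9.4% | 1.9 | 11.9% |

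Simulated t-tests with 100 patients per study give 17.2%, 15.6% and 13.0% at ρ = 0.3, 0.5 and 0.7. If correlation decays with distance between visits (first-order autoregressive, adjacent correlation 0.5 to 0.8), the range is 16.6% to 12.7%.

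**After a fix.** One pre-named visit or one overall contrast has a 5% error rate. Bonferroni at 0.05/4 = 0.0125 per visit gives at most 5%, and 1 − 0.9875⁴ = 4.9% if visits are independent.

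**Precision of an averaged contrast.** The standard error of a four-visit mean, relative to one visit, is √((1 + 3ρ)/4) = √(2.5/4) = 0.79 at ρ = 0.5. Assume 85 patients per study and a difference of 0.35 SD:
- One pre-named visit: SE = √(2/85) = 0.153; 0.35/0.153 = 2.28; power = Φ(2.28 − 1.96) = 63%.
- Mean of four visits, same difference at every visit: SE = 0.153 × 0.79 = 0.121; 0.35/0.121 = 2.89; power = Φ(2.89 − 1.96) = 82%.
- Mean of four visits, with the difference present at only one, two or three visits: the averaged difference is 0.0875, 0.175 or 0.2625 SD, and power is 11%, 30% or 58%.

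**The case against.** The strongest reply is that the plan nowhere announces four tests. Its sentence fits a single visit, or a single summary per patient, equally well. That stands: per-visit testing is a natural reading of the sentence, not stated text. A reader might infer that the chance of a false blinding effect is about three times 5%. The documents do not support that as a fact. It is a mid-range value that needs a test level, a correlation, a shared visit schedule and an any-visit rule, and none of these is given. Section 2.3 says the two designs are the same, but no AxA pain schedule appears. Section 1 reports AxA DEXA scanning between 3 and 6 months, while Table 7.1 here has no 6-month visit, so identical schedules cannot be taken for granted.

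A reader might also infer that averaging always gains power. It does not. The rise from 63% to 82% is relative to one pre-named visit and needs a constant effect. On the same inputs, counting any of four visits gives 89% power, though at the inflated error rate.

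The comparison is also one of five secondary objectives, with no power calculation and no stated success criterion. That limits how serious the gap is. It does not remove it: even if a single test is intended, the plan does not say which one.

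Finally, multiplicity is not the only problem. The two cohorts were not randomised against each other, so a 5% error rate for a difference between studies is not a 5% error rate for an effect of blinding. This stands in full.

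**Conclusion.** The gap is real. A two-sample test is assigned to a score with up to eight postoperative values per patient, and no section names the visit, the crest score or an overall contrast. Section 9.4 does not close the gap, because its repeated-measures analysis serves change over time.

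The consequence is conditional: a false-positive chance of about 9% to 18.5% over four visits (about 16% at correlation 0.5), and about 25% at that correlation if both crests are tested. Every such figure rests on the four assumptions listed with the inputs.

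Two limits apply. A difference between this study and AxA is not by itself attributable to blinding. The exposure is also unclear: section 2.3 says patients will not be blinded to the donor site, while section 7.2 says the harvest side is not communicated to them. Until these sections are reconciled, it is not settled that the two cohorts differ in what the comparison is meant to test. The point concerns a secondary objective and leaves the primary result untouched, but it should be corrected before the data are compared.

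**What to change.** In section 9.3 item 4:

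1. Define one score per patient per visit, for example the VAS of the crest on the harvest side, which CRF B records.
2. Fit the type of repeated-measures model already planned for VAS in section 9.4, with study, visit and study-by-visit terms.
3. Test once, at two-sided 5%, the study difference averaged over the postoperative visits common to both trials. List those visits after checking the AxA schedule.
4. Report visit-specific differences with confidence intervals as descriptive.
5. State that the comparison is non-randomised and between studies, so a difference cannot be attributed to blinding alone.
6. Reconcile section 2.3 item 4 with section 7.2 on what patients are told about the harvest side.

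If an effect is expected at only some visits, name one deciding visit in the plan instead and label the others exploratory.

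The cost is plan wording and one model fit, with no new data collection in this study. The statistical price is that the averaged contrast loses power when the effect is confined to some visits.

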9.4 Other study parameters

The following information will be reported and reviewed, but will not influence the comparisons between the treatment conditions as this is an intra-patient model.

- Demographics
- Nicotine use
- Pre-operative diagnosis
- Medical history
- Concurrent medical issues
- ASA classification
- Disease related medication use
- NSAID use
- Perioperative data
- Length of hospital stay
- EQ-5D-5L
- ODI
- Pain drawing
- NRS satisfaction

The clinical outcome measures, the EQ-5D-5L, ODI and VAS, will be analyzed with repeated measurements to assess changes over time. For continuous data, an independent t-test or Mann Whitney U test (depending on the distribution of the data) will be used to compare the

clinical outcomes of fused and non-fused patients. For categorical data, the Chi-square test will be used. A logistic regression analysis will be performed to analyze the effects of smoking and NSAID use on fusion status.

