7.1.3 Other study outcomes

This study provides the opportunity to further investigate several outcomes in a cohort of 100 spondylodesis patients, not related to the comparison of MagnetOsTM Granules and autograft.

1. Changes in EQ-5D-5L, ODI and VAS pain scores over time;
2. Relation between clinical outcomes and fusion status at one-year follow-up;
3. Satisfaction with treatment;
4. Effect of nicotine use on fusion;
5. Effect of NSAID use on fusion.

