7.2 Randomization, blinding and treatment allocation

Randomization for the allocation of the graft type will be performed with use of a computerized random-number algorithm. The randomization scheme will be maintained at the UMC Utrecht by the central principal investigator and study coordinator. The orthopaedic surgeon will be blinded to the allocation side of MagnetOsTM Granules, and thereby the contralateral allocation of autograft, as long as possible. He/she will receive an envelope containing the randomization of the patient which should be opened during surgery just

before the graft is needed (see suggested surgical technique, Appendix B). The iliac bone graft has to be taken from the same side where the autograft will be applied for posterolateral fusion according to the randomization. This will not be communicated to the patient. Whenever possible, bone harvesting will be done without making an additional skin incision.

In case an intra-operative decision is made to perform something different than what was intended for study enrollment, like for example to use local bone graft only or an uninstrumented spinal fusion, the patient will be considered a per-operative withdrawal and will not be treated with MagnetOs™ Granules. These patients will be replaced as described in paragraph 7.5.

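### The comparison of clinical scores between fused and non-fused patients names no covariate and does not say whether one-year scores or changes are tested, although pre-operative scores are collected

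*Combined protocol and SAP*

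**What the plan says.** Section 7.1.3 lists "Relation between clinical outcomes and fusion status at one-year follow-up" among the other study outcomes, which it separates from the graft comparison.

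Section 9.4 gives the method for continuous measures: "an independent t-test or Mann Whitney U test (depending on the distribution of the data) will be used to compare". The two groups in question are those who fused and those who did not. Categorical data get a Chi-square test. The section names no covariate for this comparison. It does not say whether the tested variable is the one-year score or the change since surgery.

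Section 7.3.1 states that "a preoperative baseline evaluation will be performed and the following data will be collected", and the list includes EQ-5D-5L, ODI and VAS pain. Section 7.3.3 repeats these at one year. The satisfaction NRS is added only at follow-up, so it has no baseline.

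Two other analyses in section 9.4 come close. The clinical scores "will be analyzed with repeated measurements to assess changes over time", with no mention of fusion status. A logistic regression on smoking and NSAID use has fusion status as its outcome. Neither is described as adjusting the fused versus non-fused comparison.

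**The concern.** Section 7.2 says "Randomization for the allocation of the graft type will be performed with use of a computerized random-number algorithm". That allocates a graft to a side within each patient. It does nothing to balance patients who fuse against patients who do not, because those groups are formed by a postoperative result. Section 9.4 says that demographics, diagnosis, ODI and similar items will not influence the treatment comparisons because the model is intra-patient. That argument covers MagnetOs versus autograft within a patient. It does not cover a contrast between patients.

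The plan itself expects fusion to vary with patient characteristics. Section 2.3 proposes to relate pseudoarthrosis to comorbidities, smoking and construct length. If fused and non-fused patients also start from different scores, a two-sample test mixes that difference with any relation to fusion. Even without such a gap, the test leaves unused a covariate that would narrow the confidence interval.

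At stake are the precision and interpretability of an exploratory result. No patient-level definition of fused is given either. Section 7.4.2 and Appendix C score segments, while section 9.1 and Appendix A give a relative score per side. Any analysis of fused patients needs that definition first.

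**Working it through.** **The plan's own figure.** The only sample size in the documents is for the primary paired test: 84 evaluable patients, 100 enrolled. With 30% discordance, a margin of 0.15, one-sided alpha 0.05 and 80% power, the simple formula gives (1.645 + 0.842)² × 0.30 / 0.15² = 82.4, so 83. The exact power of the paired score test at n = 84 is 0.80098, as in the Appendix A table. Then 84/0.85 = 98.8, so 100 enrolled is consistent. This figure is not in dispute. The documents give no size, alpha or power for the fused versus non-fused comparison.

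**Inputs for this comparison**
- From section 4.4: 50% fusion per side, 70% concordance, 15% not evaluable.
- Both sides fused: 0.50 − 0.30/2 = 0.35. At least one side fused: 1 − 0.35 = 0.65. The groups split 65:35 whether fused means either side or both.
- Evaluable patients: 0.85 × 100 = 85, split about 55 and 30.
- Assumed, not in the documents: r = 0.4 to 0.6 between baseline and one-year scores, equal variances at both times, two-sided 0.05, and a possible baseline gap of 0.5 SD between the groups.

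**Formulas (variances relative to the one-year score)**
- One-year score, unadjusted: 1. Change score: 2(1 − r). Baseline-adjusted: 1 − r² when the groups do not differ at baseline.
- Gain against the one-year score: 1/(1 − r²) − 1.
- Gain against the change score: 2(1 − r)/(1 − r²) − 1 = 2/(1 + r) − 1.
- A baseline gap d multiplies the adjusted variance by about 1 + d² × 0.65 × 0.35. For d = 0.5 this is 1 + 0.25 × 0.2275 = 1.057. For d = 0.25 it is 1.014, which is trivial.
- Shift in the unadjusted result when fusion has no relation to outcome at a given baseline score: r × d for one-year scores, (r − 1) × d for change scores.

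| r | 1 − r² | Gain vs one-year score, no gap | Gain vs one-year score, 0.5 SD gap | Gain vs change score, no gap | Shift, one-year score, 0.5 SD gap | Shift, change score, 0.5 SD gap |
|---|---|---|---|---|---|---|
| 0.4 | 0.84 | 19% | 13% | 43% | +0.20 SD | −0.30 SD |
| 0.5 | 0.75 | 33% | 26% | 33% | +0.25 SD | −0.25 SD |
| 0.6 | 0.64 | 56% | 48% | 25% | +0.30 SD | −0.20 SD |

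Gains are expressed as equivalent extra patients.

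**What this means at 55 versus 30.** The unadjusted standard error is √(1/55 + 1/30) = 0.227 SD. The difference detectable with 80% power is (1.960 + 0.842) × 0.227 = 0.64 SD. Multiplying by √(1 − r²) gives 0.58, 0.55 and 0.51 SD for r = 0.4, 0.5 and 0.6.

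**Simulation check.** In 20,000 simulated trials per setting, with one-year scores, no true relation to fusion and a 0.5 SD baseline gap, the t-test rejected in 10%, 19% and 33% of trials for r = 0.3, 0.5 and 0.7. The baseline-adjusted model rejected in about 5% and had bias of about zero. The baseline score was the only confounder simulated, so this shows what adjustment does for that one source.

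**The case against.** A reader might infer that the plan ignores the baseline value. The documents do not establish this. Section 9.4 speaks only of clinical outcomes, and the sentence before it concerns change over time. A t-test on change scores would use the baseline. This objection stands: what can be said is that the tested variable is unspecified and no covariate is named. Adjustment is more precise than either version for the assumed r, but the size and direction of the effect depend on which is meant.

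A reader might also infer that adding the baseline score removes the confounding. It does not. Smoking, number of levels, diagnosis and interbody fusion would remain unadjusted, and satisfaction has no baseline to adjust for. This also stands, and it limits what the fix can claim.

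Third, the stated aim is a relation. No causal claim or decision rule is attached, and section 3 itself says that clinical outcome does not really reflect fusion, especially in the first years. It would therefore go too far to say that the plan attributes a baseline difference to fusion. That is a reason for modest severity. It is not a reason to prefer the less precise analysis when the covariate is already in the database.

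**Conclusion.** The point holds as an inexpensive improvement to an exploratory analysis. The comparison is between non-randomised groups, the tested variable is not specified, no covariate is named, and baseline values exist for EQ-5D-5L, ODI and VAS.

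All sizes rest on an assumed r of 0.4 to 0.6. The gain is about 19% to 56% more patients against one-year scores with no baseline gap, about 13% to 48% with an assumed 0.5 SD gap and a 65:35 split, and about 43% to 25% against change scores with no gap. Whether any gap will exist is unknown, so the shifts shown above are conditional and not predicted.

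It would be wrong to read this as a threat to the trial's main result. The primary paired comparison, its sample size and the safety assessment do not use this analysis.

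**What to change.** In section 9.4, for EQ-5D-5L, ODI and VAS, do one of the following:
- replace the two-sample tests with a linear model of the one-year score on fusion status, with the baseline score as covariate; or
- add fusion status and its interaction with time to the planned repeated-measures model, with baseline handled as a covariate or as part of the outcome vector.

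Use robust or bootstrap standard errors if residuals are skewed, so that the protection sought from the Mann-Whitney option is not lost. Keep the two-sample test for NRS satisfaction.

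State the patient-level definition of fused: one side or both, and all evaluable levels or any. Report the result as an association. Smoking, number of levels, diagnosis and interbody fusion are already recorded and can be added as a pre-specified sensitivity analysis.

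The cost is a few sentences of analysis-plan text. No new data, visits or patients are needed.
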